7.2. Demographics and other baseline characteristics

Subject demographics (e.g. age and sex), oral care habits (e.g. flossing and smoking) and baseline characteristics (e.g. MGI, BOP and PI) will be presented by treatment group and in total. Measurements of recorded teeth with calculus will not be included in statistical analysis.

7.3. Significance level

Unless stated otherwise, significance level is 0.05. A p-value may be complemented by confidence interval.

7.4. Method

Reductions in gingivitis – BOP, MGI and PPD – and plaque – PI from baseline scores after 2 weeks, 4 weeks and 12 weeks of use will be evaluated. For each subject, mean score of each index will be calculated as well as reductions from baseline at three time points. Additionally, numbers of abrasion sites found will be compared.

Assuming evaluated scores for the test and control groups are denoted U_{Test} and U_{Control} , respectively, the null hypothesis will be tested.

$$H_0: U_{\text{Test}} - U_{\text{Control}} = 0$$

$$H_1: U_{\text{Test}} - U_{\text{Control}} \neq 0$$

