4.3. Primary endpoint

The primary endpoint of this study is reduction of gingivitis (change from baseline) as measured by BOP and MGI at baseline, and again at 12-week visits.

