4.5. Study procedure

The study to be conducted will be single-blinded, randomized controlled, parallel design. The study population will consist of Seventy-two (72) male and female subjects conforming to the following admission criteria. The subjects meeting the admission criteria with an anticipation of 40% dropout rate will be stratified into two groups balanced for MGI, BOP, PI, and gender using screening data. In this single-blind design, product assignment will be randomized after screening, and only the PI and the Study coordinator will have access to the randomization key.

One group will be assigned to a new power toothbrush while the control group will be assigned an ADA approved manual toothbrush. The study involves a 12-week home use of the respective toothbrushes. Both groups will refrain from the regular use of mouthwash and any interdental device, such as floss, floss picks, toothpicks, water flossing device or interdental brush, during the length of the study. Written instructions on brushing and professional brushing demonstration will be provided at the outset of the study and each participant from both test and control groups will also receive a 2-minute timer to help them monitor their brushing time. Before each visit, subjects are expected to have at least 7 hours, but no more than 12 hours of accumulated, non-brushed, undisturbed plaque/debris.

The study includes four or five visits – screening, baseline, 2-week follow-up, 4-week follow-up and 12-week follow-up. Schematic 1 summarizes the study procedure and visits and Table 2 details procedures in this study. The Screening and the baseline visit may happen on the same day.

Schematic 1. Study and visit procedures

CONFIDENTIAL

CONFIDENTIAL

Visit 2: Baseline
(continued)

A

Use brush per instruction

PI examination after
brushing

Single use
result

Schedule next visit

Pre visit

7 – 12 hours of plaque
accumulation

Visit 3: Follow-up visit
at 2 weeks

Oral examination for tissue abrasion and MGI
by calibrated examiners

Periodontal probing for BOP and PPD
by calibrated examiners

Oral examination for PI
By calibrated examiners

Schedule next visit

Pre visit

7 – 12 hours of plaque
accumulation

Visit 4: Follow-up visit
at 4 weeks

[figure not shown]
Oral examination for tissue abrasion and MGI
by calibrated examiners

Periodontal probing for BOP and PPD
by calibrated examiners

Oral examination for PI
by calibrated examiner

Schedule next visit

A

CONFIDENTIAL

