At the screening exam, subjects will receive an oral soft tissue exam with periodontal probing, modified Gingival Index on the Ramfjord teeth, and the amount of stain and calculus will be noted. Following these examinations, the subject's plaque will be disclosed with Trace 28 solution (4 drops under tongue) and they will swish for 10 seconds. Next, subjects will rinse with 10 ml. of tap water twice for 10 seconds each. Disclosed plaque will then be recorded on buccal and lingual surfaces of the Ramfjord teeth using the Lobene modification of the Turesky Plaque Index. If baseline happens on the same day then full mouth GI and BOP will be carried out prior to disclosing for full mouth plaque measurements. Subjects who meet the admission criteria will be allowed to enroll. If a subject fails the screening exam due to oral disease such as, but not limited to dental caries and periodontitis, the subject will be appropriately referred to the main Marquette University School of Dentistry (MUSoD) screening clinic to insure that they will be given an opportunity for full diagnosis and treatment at the school of dentistry or some other appropriate clinic.

Each clinical index will be scored by one of two or three calibrated examiners. The oral cavity/oral safety exam and all measures of inflammation, the MGI, PPD and BOP will be carried out by examiners #1 and 2 while disclosing and scoring of the PI will be scored by examiners #3 and 4. A fifth examiner who is dual calibrated will be used if needed. Each examiner will be calibrated to the indices used, and will demonstrate repeatability of measures initially at the screening/calibration phase as well as during the study.

Visit 2: Baseline

Subjects who have signed consent form and met all the inclusion criteria and none of the exclusion criteria will be entered into the baseline procedure (day 0). This visit may occur the same day as screening.

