7. STATISTICAL ANALYSIS

Each of the two research groups' patients will be assessed clinically at four time points (Baseline, 2 weeks, 4 weeks and 12 weeks). These measures will be compared against one another and over time using a between-within factors repeated measures ANOVA.

Further evaluation of interproximal and marginal scores will also be evaluated with a post hoc analysis.

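### BOP and MGI are compared as change from baseline with no baseline covariate; adjusting for the full-mouth baseline score already collected would usually be more precise

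*Combined protocol and SAP*

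**What the plan says.** Section 4.3 defines the primary endpoint as "reduction of gingivitis (change from baseline) as measured by BOP and MGI at baseline, and again at 12-week visits". Section 7.4 carries this into the analysis: "For each subject, mean score of each index will be calculated as well as reductions from baseline at three time points". It then gives a two-sided null hypothesis of no difference between test and control.

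Section 7 lists baseline, 2, 4 and 12 weeks as the assessment times and says "These measures will be compared against one another and over time using a between-within factors repeated measures ANOVA". Baseline is therefore a level of the outcome. The only other stated use of the baseline scores is descriptive (section 7.2): "baseline characteristics (e.g. MGI, BOP and PI) will be presented by treatment group and in total".

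Two design features matter here. Section 4.5 says subjects will be "stratified into two groups balanced for MGI, BOP, PI, and gender using screening data". Under Visit 2 of the same section, full-mouth MGI, probing depth, BOP and plaque are scored before the subject goes to receive a brush.

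**The concern.** A comparison of change scores is a baseline-adjusted comparison in which the slope of follow-up on baseline has been set to 1 in advance. The repeated measures ANOVA does not escape this. Its group-by-time contrast between baseline and week 12 is the difference in mean change, and its group main effect averages in a visit at which no brush effect can exist.

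Gingival scores carry examiner error and vary within a subject over time, so the slope is usually below 1. Subtracting the whole baseline then has two effects. It adds noise that an estimated slope would not add. It also removes too much of any chance baseline difference, so the arm that starts worse tends to show the larger reduction. At stake are the precision of the primary comparison and its sensitivity to chance imbalance, in a trial that plans for about 44 evaluable subjects.

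**Working it through.** **Inputs from the documents.** Section 7.1: alpha 0.05, power 0.95, 44 evaluable (22 per arm), 40% dropout, 72 enrolled. Section 7.4: two-sided test. No effect size, SD or baseline-to-week-12 correlation is given.

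**Assumptions.** Correlation r from 0.3 to 0.7. Ratio k of week-12 SD to baseline SD: 1 in the main case, 1.3 as a variant.

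**The plan's own figure.** 44/(1 − 0.40) = 73.3, so 74 against 72 stated; 72 × 0.60 = 43.2. This is close agreement. The 44 itself cannot be reproduced without an effect size. Solved backwards with the normal approximation, 22 per arm at 95% power implies a standardised difference of (1.960 + 1.645) × √(2/22) = 1.09.

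**Variance with equal SDs (k = 1), in units of the score variance**

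- Change score: 2(1 − r)
- Baseline-adjusted: 1 − r²
- Ratio of adjusted to change: (1 + r)/2

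| r | Change | Adjusted | Ratio | Saving |
|---|---|---|---|---|
| 0.3 | 1.40 | 0.91 | 0.65 | 35% |
| 0.5 | 1.00 | 0.75 | 0.75 | 25% |
| 0.7 | 0.60 | 0.51 | 0.85 | 15% |

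An unadjusted week-12 comparison has variance 1 on this scale. At r = 0.3 the change score is therefore less precise than ignoring baseline. At r = 0.9 the saving is only 5%.

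**Variance with unequal SDs.** The ratio is (1 − r²)k²/(1 + k² − 2rk). At k = 1.3, k² = 1.69:

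- r = 0.3: 1.538/1.91 = 0.805, saving about 19%
- r = 0.5: 1.268/1.39 = 0.912, saving about 9%
- r = 0.7: 0.862/0.87 = 0.991, saving about 1%

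The slope is b = rk, here 0.39, 0.65 and 0.91. The excess variance of the change score is (1 − b)² times the baseline variance, which vanishes as b approaches 1.

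**Power.** Suppose the 95% at 22 per arm refers to the change score, with k = 1. The standardised shift 1.960 + 1.645 = 3.605 is divided by the square root of the ratio. Subtracting 1.960 gives 2.51, 2.20 and 1.95, so power is 99.4%, 98.6% and 97.4% at r = 0.3, 0.5 and 0.7. Equivalently, 95% power would need 22 × 0.65 = 14.3, 22 × 0.75 = 16.5 and 22 × 0.85 = 18.7, that is 15, 17 and 19 per arm.

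**Chance imbalance.** With k = 1, if one arm starts higher by D, its reduction is overstated by (1 − r)D. Without balancing, one standard error of D at 22 per arm is √(2/22) = 0.30 SD. The distortion is then 0.21, 0.15 and 0.09 SD at r = 0.3, 0.5 and 0.7.

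**Effect of balancing on the standard error.** Take the limiting case of perfect balance on the baseline score, again with k = 1. The true variance of the contrast is the adjusted one, while the unadjusted analysis still reports the larger change-score variance. The nominal cut-off of 1.96 then acts as 1.96/√0.65 = 2.43, 1.96/√0.75 = 2.26 and 1.96/√0.85 = 2.13, so a nominal 5% test has a true size of about 1% to 3%.

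**The case against.** **Validity.** Change from baseline is the declared endpoint, and under randomisation its comparison is unbiased on average. This stands. A reader might infer that the primary result is biased; the documents do not support that.

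**Balancing.** Section 4.5 balances the arms on screening MGI, BOP, plaque index and gender, and screening and baseline may fall on the same day. This limits chance imbalance, so the distortions above, computed without balancing, are larger than should be expected. The balance is still imperfect: the screening exam scores "modified Gingival Index on the Ramfjord teeth", whereas the endpoint is full-mouth, and 40% dropout can disturb balance among completers. Balancing on prognostic scores and then omitting them also makes the reported standard error too large, which is a further reason to adjust.

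**Entry thresholds.** A reader might infer that selection on MGI and BOP (section 5.1) is what pushes the slope below 1. It is not: under a linear relation, selecting on baseline leaves the slope of follow-up on baseline unchanged. The MGI and BOP criteria are also joined by and/or, so neither index need be truncated in every subject. The BOP band of 20% to 50% could restrict baseline spread, which makes k above 1 plausible and the gain smaller.

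**Comparator.** The omnibus group-by-time test of the section 7 ANOVA uses all visits and a pooled error term. The variance figures here apply to the baseline-to-week-12 contrast, which is the primary endpoint, and not to that omnibus test.

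**Conclusion.** The plan names no baseline covariate for BOP or MGI, and adding one would usually improve precision. The saving in variance is 15% to 35% if the SDs are equal and r lies between 0.7 and 0.3. It is about 1% to 19% over the same range if the week-12 SD is 1.3 times the baseline SD. These are conditional figures, because the documents give neither the correlation nor the SDs.

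Two other strong readings should be resisted. First, baseline differences are not left uncorrected; subtraction corrects them too far when the slope is below 1. Second, a reader might infer that the trial is seriously underpowered. If the 95% had been planned for an adjusted analysis, the change score would have 82.8%, 87.7% and 91.4% power at r = 0.3, 0.5 and 0.7, but no adjusted analysis is planned. Larger gains can be obtained by assuming a smaller effect, but the documents give no effect size. On the reading that fits the text, power moves from 95% to about 97-99% under equal SDs.

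This is an inexpensive improvement to a valid analysis.

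**What to change.** In sections 7 and 7.4, make the primary analysis of BOP and of MGI a linear model for the week-12 score. Covariates are arm, the subject's full-mouth baseline value of the same index, and the balancing factors (screening MGI, BOP and plaque index, and gender). Alternatively, use a mixed model on weeks 2, 4 and 12 with the same covariates and a stated week-12 contrast. Either way, say that this replaces the ANOVA in which baseline is an outcome level.

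Use the same form for plaque index and probing depth. For single use, model the post-brushing plaque index on the pre-brushing value. State the assumed baseline-to-week-12 correlation with the sample size. Mean reductions can still be reported descriptively, and the arm effect stays on the same scale.

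The cost is analysis wording and a few degrees of freedom. With 44 evaluable subjects and one term for each covariate, the residual degrees of freedom go from 44 − 2 = 42 to 44 − 2 − 1 − 4 = 37. No new data, visits or subjects are needed.

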3.2. Secondary objectives

Secondary objectives are to evaluate the following:

- Effectiveness on plaque removal

CONFIDENTIAL

- Hard and soft tissue damage

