4. STUDY DESIGN

4.1. Clinical Parameters

4.1.1 Oral Cavity Exam/Oral Safety Exam

4.1.2 Modified Gingival Index[3]

4.1.3 Lobene Modified Turesky Plaque Index[4,5]

4.1.4 Full mouth periodontal charting of pocket depths and Bleeding Index

4.2. Description of Clinical Parameters

4.2.1. Oral cavity examination

Oral cavity examination for safety assessments will include evaluation of the lips, tongue, hard and soft palate, gingiva, all mucobuccal fold areas, inner surface of the cheeks and sublingual areas, tooth surfaces and restoration surfaces. All areas will be assessed and reported as normal or abnormal with an explanation of any abnormality. In particular, the cervical root area will be carefully examined.

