4.4. Secondary endpoints

The following indices and parameters are secondary endpoints.

- Reduction of BOP and MGI at two-week, four-week visits from the baseline
- Reduction of PPD at 2-week, 4-week and 12-week visits from the baseline
- Reduction in plaque by measuring PI at 2-week, 4-week and 12-week visits as well as after a single use
- Safety of the product: clinical examiners inspect for any hard or soft tissue damage
- Patient reported outcomes from an exit survey and user diary

[figure not shown]
CONFIDENTIAL

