In this visit, subjects will first be evaluated for signs of soft or hard tissue trauma, and then full mouth Modified Gingival Index followed by full mouth probing of pocket depth and assessment of BOP. Teeth with calculus will be recorded. After these data are recorded each subject will be disclosed and full mouth Plaque scores assessed and recorded by a calibrated examiner. Any scorable teeth that have plaque buildup on any six tooth sites will be recorded. The subjects will then leave the examining area to the randomization and toothbrush distribution area where they will be provided their assigned brush out of site of the examiners. Group A will be given a power toothbrush, while Group B will be given a manual toothbrush. Both groups will also be given a two minute timer and the same fluoride toothpaste (Colgate Cavity Protection toothpaste) as well as the appropriate set of written instructions on tooth brushing. The subjects in the test group will follow the instructions provided by the manufacturer, while subjects in the control group will be given a standard written and both groups provided visual instructions on proper brushing. A study staff member will be available to answer any questions pertaining to the instructions and coach patients toward optimal brushing technique. Then the subjects will be required to use the brush assigned for two minutes before being sent back to the examiner to

CONFIDENTIAL

have a post-brushing plaque index recorded. These pre- and post 2-minute brushing data will be collected to assess single use effect differences between the toothbrush types. Subjects will be reappointed and instructed to bring their assigned brush to the subsequent exam sessions in a brown bag to avoid unmasking any of the examiners.

Visit 3: Two-week follow-up

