The first follow-up will take place two weeks after the baseline visit. Subjects can schedule the visit for any time between two days before and after the two-week use period (12-16 day range). Clinical examinations will be given to the subjects in the same order as the baseline visit with the exception that no second plaque index will be recorded. All subjects must present with 7 to 12 hours of undisturbed plaque. The oral safety exam will include a thorough examination of the gingiva to look for any signs of gingival trauma, irritation or abrasion. Any subjects who show signs of gingival trauma that appears to be toothbrush related will be exited from the study. The recorded findings will be reported as Adverse Events. In addition, any site in the mouth that shows an increase in probing pocket depth of 2 mm or greater from the baseline measurement will have that particular site treated with subgingival scaling and root planing or whatever the PI deems appropriate therapy. If subjects meet any of the discontinuation criteria, they will be withdrawn from the study.

Visit 4: Four-week follow-up

This visit should take place four weeks after the baseline visit within three days before and after the four week mark (25-31 day range). Subjects will receive full mouth examinations in the same order as the previous visit. Additionally, inspection for signs of gingival trauma and increase in PPD greater than 2 mm from the baseline will be conducted and evaluated. The PI will determine if any subject meets the discontinuation criteria as well as appropriate therapy to treat.

Visit 5: 12-week follow-up

In this visit, subjects will return the products, including manual toothbrush, or brush head, brush handle, and charger. The procedure is similar to the four-week follow-up visit, in which full mouth clinical examination will be carried out as before on each of the subjects. The subjects' disclosed plaque will be evaluated as usual. The examined results will be recorded. Prophylaxis will be carried out as needed.

The used brushes/brush heads will be returned to sponsor at the end of the trial and examined for wear as an additional measure of compliance.

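### Section 7 specifies a between-arm safety comparison only for undefined abrasion sites, which is narrower than the endpoint of any hard or soft tissue damage

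*Combined protocol and SAP*

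**What the plan says.** All references are to the combined protocol and SAP.

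- **Objective (3.2).** One of the two secondary objectives is "Hard and soft tissue damage".
- **Endpoint (4.4).** "Safety of the product: clinical examiners inspect for any hard or soft tissue damage".
- **Examination (4.2.1).** Besides the soft tissues, it covers "inner surface of the cheeks and sublingual areas, tooth surfaces and restoration surfaces", and it singles out the cervical root. On recording: "All areas will be assessed and reported as normal or abnormal with an explanation of any abnormality".
- **Baseline visit (4.5, Visit 2).** "subjects will first be evaluated for signs of soft or hard tissue trauma".
- **Follow-up (4.5, Visit 3; repeated in 5.3).** The oral safety exam includes a "thorough examination of the gingiva to look for any signs of gingival trauma, irritation or abrasion".
- **Adverse events (6.4).** Changes the investigator considers possibly, probably or definitely caused by the device are recorded, with onset, action, outcome and an opinion on relationship.
- **Analysis (7 and 7.4).** Section 7 opens with a repeated measures ANOVA of the clinical measures and names no safety variable. Section 7.4 names BOP, MGI, PPD and PI, then adds one safety item: "Additionally, numbers of abrasion sites found will be compared".

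**The concern.** The objective, the endpoint and the examination share one broad definition of what matters for safety. The analysis section uses a different and apparently narrower word. If abrasion is read as it is used in the follow-up visit text, three kinds of finding fall outside the only comparison named: damage to a tooth or restoration surface, gingival trauma, and gingival irritation. They would be examined and written down, but nothing in section 7 commits the sponsor to compare them between arms.

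Safety is half of the overall study objective in section 3, which names efficacy and safety together. A power brush that caused irritation or root-surface damage but few abrasions could look no different from the manual brush in the one comparison the plan names. An undefined term also leaves the choice of what counts as an abrasion site open until after the data have been seen.

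**Working it through.** This is a question of coverage. The plan gives no safety figure to reproduce, so the check sets the sections side by side.

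| Place | What counts |
|---|---|
| 3.2, objective | Hard and soft tissue damage |
| 4.4, endpoint | Any hard or soft tissue damage |
| 4.2.1, examination | Soft tissues, tooth and restoration surfaces, cervical root; normal or abnormal, with an explanation |
| 4.5, baseline | Soft or hard tissue trauma |
| 4.5 Visit 3 and 5.3, follow-up | Gingival trauma, irritation or abrasion |
| 4.5, Schematic 1 and Table 2 | Abrasion used as a label for the whole examination |
| 6.4 | Changes judged at least possibly caused by the device are recorded |
| 7, opening paragraph | Clinical measures, with no safety variable named |
| 7.4 | Number of abrasion sites |

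**Step 1: is abrasion the same as damage?** In Visit 3 and 5.3, abrasion is one of three listed gingival signs, so there it is narrower than damage and confined to soft tissue. In Schematic 1 and Table 2 the word names the whole safety examination, so there it could be wider and could include cervical tooth abrasion. No definition settles which use 7.4 intends.

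**Step 2: does another part of section 7 fill the gap?** The opening paragraph might take in the oral cavity exam, because 4.1.1 lists that exam as a clinical parameter. But it names no safety variable, and a repeated measures ANOVA is not a natural method for normal or abnormal findings. Section 7.4 does name PPD, but as a reduction to be evaluated, not as damage. Section 6 sets rules for recording and reporting, with no tabulation or comparison by arm.

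**Step 3: size.** The documents give no rate for any kind of damage and no split between abrasions and other findings. The loss therefore cannot be computed from them.

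**Step 4: a check on the remedy.** Counting every abnormality at follow-up, whether or not it was present at baseline, would carry its own cost. For illustration only, assume brushing damage in 5% of manual and 30% of power subjects, plus an unrelated abnormality with probability *u* in both arms, independent of the damage. The observed risk is then 1 − (1 − p)(1 − u). Power is from exact enumeration of the two-sided Fisher test at 0.05, with the 36 subjects per arm enrolled under 7.1.

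| u | Manual | Power brush | Difference | Power of test |
|---|---|---|---|---|
| 0 | 5.0% | 30.0% | 25.0 points | 76% |
| 0.10 | 1 − 0.95 × 0.90 = 14.5% | 1 − 0.70 × 0.90 = 37.0% | 22.5 points | 50% |
| 0.20 | 1 − 0.95 × 0.80 = 24.0% | 1 − 0.70 × 0.80 = 44.0% | 20.0 points | 34% |
| 0.30 | 1 − 0.95 × 0.70 = 33.5% | 1 − 0.70 × 0.70 = 51.0% | 17.5 points | 23% |

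These rates are assumptions, and 7.4 does not specify this test. The table shows only why the added comparison should count findings that are new or worse than at baseline.

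**The case against.** The strongest reply is that abrasion is this protocol's shorthand for everything the safety exam finds. Schematic 1 and Table 2 use it that way, and 4.2.1 draws attention to the cervical root, where a tooth surface can be abraded. On that reading, abrasion sites in 7.4 could include hard tissue. This stands in part. A reader might infer that the planned comparison captures no hard-tissue damage at all, and the documents do not establish that. But the shorthand is never stated, and the follow-up text uses the word in a narrower sense.

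A reader might also infer that the other findings will never be compared. That is too strong: the opening of section 7 is loose enough to include the oral cavity exam. What can be said is that no such comparison is clearly specified.

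Nor can it be said that other findings vanish or count for nothing. Gingival trauma that appears toothbrush-related leads to exit from the study and an adverse event report (4.5, 5.3), and 6.4 requires device-related changes to be recorded. That is recording, not comparison, and 6.4 depends on the investigator's attribution.

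Finally, a reader might infer from 4.2.1 that the exam form cannot yield a count of sites. The form is not in the documents, and the required explanation of each abnormality could give its type and location. That inference is not supported.

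**Conclusion.** The mismatch is real and should be corrected. The objective, endpoint and examination cover any hard or soft tissue damage, while the one safety comparison named in section 7 uses an undefined term that, where the text ties it to a tissue, means one kind of gingival finding. As the plan stands, no between-arm comparison is clearly specified for hard-tissue damage or for soft-tissue damage other than abrasion.

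The consequence is moderate. The examination is planned at every visit, so the information can still be analysed, and no efficacy result is affected. It would go too far to say that the trial cannot answer its safety question. How much sensitivity is lost depends on damage rates and on the share of damage that is abrasion, and the documents give neither. The conclusion rests on the wording of the sections compared above and on no assumed rate.

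**What to change.** In 7.4, keep the abrasion site comparison and define an abrasion site, stating which tissues count. Then add:

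> The number and proportion of subjects with any hard or soft tissue abnormality at the oral cavity examination (4.2.1) that is new or worse than at baseline, at any follow-up visit, will be compared between groups with a confidence interval, overall and separately for soft tissue and for hard tissue (tooth, cervical root and restoration surfaces).

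The cost is a wording change and one extra table. Study procedures do not change, because Table 2 already schedules the examination at baseline and at each follow-up visit. The downside is that some new abnormalities will have nothing to do with brushing and will add noise. The baseline reference removes those already present and unchanged. The breakdown by tissue, together with the investigator's view of relationship to the device recorded under 6.4, will help show the rest.

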1. SELECTION AND WITHDRAWAL OF SUBJECTS

5.1. Admission Criteria

A subject who meets all the following criteria will be eligible to enroll in this study.

1. Age range 18 – 65 years
2. Routine manual toothbrush user
3. A Subject who agrees to use the assigned toothbrush as the only cleaning device for the study duration, refraining from daily interdental cleaning and/ or antiseptic mouthrinsing.
4. Mild to moderate gingivitis as measured by
 - A. Modified Gingival Index (MGI) average score of at least 1.2, and / or
 - B. Bleeding on Probing (BOP) of at least 20% of all sites but not more than 50% of sites.

CONFIDENTIAL

5. Probing Pocket Depth (PPD) of 4 mm or lower
6. At least 20 natural teeth – scoreable (crowns or bridgework are non-scoreable).

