5.3. Discontinuation criteria

The oral safety exam at the follow-up visits will include a thorough examination of the gingiva to look for any signs of gingival trauma, irritation or abrasion, as well as a periodontal probing. Any subjects who show signs of gingival trauma that appears to be toothbrush related will be exited from the study and the findings reported as Adverse Events. In addition, subjects may be discontinued due to the following reasons.

1. Voluntary discontinuation: subjects are free to discontinue their participation in the study at any time.
2. Safety concerns: the principal investigator may terminate a subject's participation if gingival trauma occurs and appears to be toothbrush related
3. Significant non-compliance to protocol: the principal investigator may terminate a subject's participation if subjects are shown to be non-compliant to the protocol
4. Incorrect enrollment: subjects who did not meet admission/exclusion criteria
5. Subject received any type of dental treatment/care other than those required in the study, for example use of interdental devices, mouthrinses, chewing gum or prophylaxis treatment, without consent of the investigator

Subjects who discontinue should be asked to a follow-up visit to observe any Adverse Events.

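### Section 7.4 compares abrasion sites at follow-up without reference to the Visit 2 trauma exam, so lesions present at entry can dilute the safety comparison

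*Combined protocol and SAP*

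**What the plan says.** Hard and soft tissue damage is a secondary objective (Section 3.2) and a secondary safety endpoint (Section 4.4). The only analysis sentence for it is in Section 7.4: "Additionally, numbers of abrasion sites found will be compared". The same paragraph says of the clinical indices that, for each subject, "mean score of each index will be calculated as well as reductions from baseline at three time points".

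A baseline reference exists. Table 2 in Section 4.5 schedules the oral cavity abrasion exam at screening, baseline and all three follow-up visits. At Visit 2, before any brush is handed out, "subjects will first be evaluated for signs of soft or hard tissue trauma". Section 4.2.1 describes the recording: "All areas will be assessed and reported as normal or abnormal with an explanation of any abnormality".

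Every subject enters as a "Routine manual toothbrush user" (Section 5.1). No criterion in Sections 5.1 or 5.2 names existing abrasion, although exclusion 14 gives general discretion over other dental conditions. The arms are balanced on MGI, BOP, PI and gender (Section 4.5), not on abrasion.

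The trauma rule, in Section 4.5 (Visit 3) and again in Section 5.3, reads: "Any subjects who show signs of gingival trauma that appears to be toothbrush related will be exited from the study". In Section 4.5 it is followed by "The recorded findings will be reported as Adverse Events". The pocket-depth rule in the same Visit 3 paragraph does name its reference: "increase in probing pocket depth of 2 mm or greater from the baseline measurement".

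**The concern.** All subjects have been brushing with a manual brush of their own, so some may arrive with gingival or cervical lesions. If the follow-up analysis counts whatever is found, old and new lesions are added together. The question for the safety objective is whether the assigned brush causes damage, and only new or worsened lesions bear on it. Old lesions carry no information about the assigned brush, but they raise the background in both arms. In a safety comparison the cost of that is a reduced chance of seeing a real difference.

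The authors wrote a baseline reference where they wanted one, for the indices and for pocket depth. Its absence for abrasion therefore leaves the outcome open to either reading.

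**Working it through.** The documents give no abrasion rate, so there is no planned figure to reproduce. The check is a comparison of texts, followed by an illustration.

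**1. Texts side by side**

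| Measure | Reference stated | Where |
|---|---|---|
| BOP, MGI, PPD, PI | Reduction from baseline | Section 7.4 |
| Pocket-depth rule | Increase from baseline | Section 4.5, Visit 3 |
| Abrasion sites | None | Section 7.4 |
| Trauma rule | None; which toothbrush is not stated | Sections 4.5 (Visit 3) and 5.3 |

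**2. Illustration of the loss of power**

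- From the documents: 36 per arm (Section 7.1), two-sided alpha 0.05 (Sections 7.3 and 7.4).
- Assumed: new lesions in a = 5% of one arm and b = 20% of the other; a share c of each arm still shows an old lesion at follow-up; old and new lesions are independent.
- Proportion of subjects with any lesion found: p1 = 1 − (1 − a)(1 − c) and p2 = 1 − (1 − b)(1 − c).
- Observed difference: p2 − p1 = (b − a)(1 − c).
- Power = Φ{[(p2 − p1) − 1.96·√(2p̄(1 − p̄)/n)] / √[(p1(1 − p1) + p2(1 − p2))/n]}, with p̄ the mean of p1 and p2.

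For c = 0: p1 = 0.05, p2 = 0.20, p̄ = 0.125. The two standard errors are √(0.21875/36) = 0.0780 and √(0.2075/36) = 0.0759. Then (0.150 − 1.96 × 0.0780)/0.0759 = −0.04, so power is 0.49.

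For c = 0.20: p1 = 1 − 0.95 × 0.80 = 0.24, p2 = 1 − 0.80 × 0.80 = 0.36, p̄ = 0.30. The standard errors are √(0.42/36) = 0.1080 and √(0.4128/36) = 0.1071. Then (0.120 − 1.96 × 0.1080)/0.1071 = −0.86, so power is 0.20.

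| c (assumed) | p1 | p2 | Difference | Power, 36 per arm |
|---|---|---|---|---|
| 0 | 0.050 | 0.200 | 0.150 | 0.49 |
| 10% | 0.145 | 0.280 | 0.135 | 0.29 |
| 20% | 0.240 | 0.360 | 0.120 | 0.20 |
| 30% | 0.335 | 0.440 | 0.105 | 0.15 |

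With 22 per arm (half of the 44 evaluable subjects in Section 7.1), power falls from 0.32 at c = 0 to 0.14 at c = 20%.

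**3. Check for bias**

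With equal true rates, a = b, the difference (b − a)(1 − c) is 0 for every c. Old lesions do not create a difference in expectation.

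**4. Unit**

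The table counts subjects with any lesion, whereas Section 7.4 compares numbers of sites. On the site scale, old lesions add the same expected number to each arm. The absolute mean difference is then unchanged, its variance rises, and the ratio between arms moves towards 1. The direction of the effect is the same, but the figures above do not transfer to site counts.

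**The case against.** **Section 7 already includes baseline.** Its opening lists baseline among four assessment times and compares groups over time with a repeated measures ANOVA. Applied to abrasion counts, that would bring baseline in. But the passage does not name abrasion, Section 7.4 is the specific text and treats abrasion differently from the indices, and neither says what makes a site new. The gap stands.

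**A reader might infer that entry lesions will be recorded as harm from the study brush.** The documents do not say so. Section 6.4 records adverse changes that the investigator attributes to the device, Section 6.1 classes an event with an implausible onset relative to device use as non-related, and Section 6.2 limits device effects to the time from first use. Misattribution would require the baseline record to be disregarded. What remains is that the trauma rule in Sections 4.5 and 5.3 does not itself refer to that record.

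**A reader might infer a false difference, because abrasion is not a balancing factor.** At 20% prevalence, the arms' difference in affected subjects has an SD of √(2 × 36 × 0.2 × 0.8) = 3.4 subjects. That is ordinary sampling variation under randomisation, and a valid test allows for it. It is noise, not bias.

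**A reader might infer that many subjects would be exited for old lesions.** An assumed 5% to 30% prevalence gives 72 × 0.05 = 3.6 to 72 × 0.30 = 21.6 subjects with an entry lesion. For all of them to be exited, every lesion would have to persist, be gingival and be judged toothbrush related. The documents support none of these steps, and hard-tissue cervical lesions fall outside the gingival trauma rule.

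**A reader might infer from Section 4.2.1 that sites cannot be counted.** That section also asks for an explanation of each abnormality, and the oral exam forms listed in the patient record are not in the text available. They may already record location.

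**Conclusion.** The point holds as a weakness in the analysis of a secondary safety outcome. Section 7.4 does not tie abrasion counts to the Visit 2 exam, so lesions present at entry can be included. The comparison stays unbiased but loses precision and contrast. The fall in power from about 0.49 to about 0.20 rests wholly on assumed rates: 5% versus 20% new lesions, and 20% of each arm with a persisting old lesion. With few entry lesions, or quick healing, the loss would be small. The primary BOP and MGI analysis is not affected by how abrasion sites are counted.

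There is also an inconsistency in the trauma wording. Section 4.5 (Visit 3) and the opening of Section 5.3 make exit mandatory, while item 2 of Section 5.3 leaves it to the investigator's discretion when trauma arises. None of the three says how a lesion already recorded at baseline is treated.

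**What to change.** - In Section 7.4, define the abrasion outcome as sites that are new or worse than at the subject's Visit 2 pre-brushing exam, or adjust for the Visit 2 count. State the visit and the unit (sites or subjects). In the illustration, perfect identification of new lesions restores the c = 0 row; adjustment for the Visit 2 count may recover less.
- Show Visit 2 abrasion counts by arm with the baseline characteristics in Section 7.2.
- If the existing oral exam form does not already do so, record abrasions by tooth and surface at every visit, so that a new site can be told from an old one.
- Reconcile Section 4.5 (Visit 3) and Section 5.3 with each other, with the Visit 2 exam in Section 4.5, and with the Adverse Event wording in Sections 6.1, 6.2 and 6.4, on how a lesion already recorded at baseline is treated. No clinical rule is proposed here.

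The cost is a change of SAP wording and, at most, slightly more recording at an exam already scheduled at every visit. No extra visit is needed.
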